Embedding research within the scope of the work of the MACH team is very important. There is a lot that remains unknown about the COVID-19 disease and meaningful inquiry about associated long term effects is an important and pressing issue.

Patients suffering with the long-term sequelae of COVID-19 disease will have a range of needs. In particular, a pressing concern for them is cognitive change. Within NHS Grampian we have heard this reported anecdotally by significant numbers of patients who have been seen in the MACH clinics so far. The prevalence of cognitive change, specifically impaired recall, has been estimated at 25% of patients from 12 to 18 months after SARS-CoV2 infection (Becker et al., 2021). In a recent large meta-analysis it was found that 32% of patients reported fatigue and 22% had evidence of cognitive impairment 12 weeks or more after SARS-CoV2 infection (Ceban et al., 2022).

We plan to offer neuropsychometric testing to all patients who report persistent cognitive symptoms in order to better understand the particular pattern, or phenotype, encountered by patients. It will be important to consider why it is that some patients report prolonged symptoms in general and prolonged cognitive symptoms specifically. Neuroimaging, and spectroscopy specifically, could start to provide answers to these questions.

The proposed project will enable research into a common adverse outcome of COVID-19 disease, which has both national recognition and significant morbidity (Ceban et al., 2022).

STUDY AIMS AND OBJECTIVES

AIMS

- To document brain structure and metabolism via spectroscopy in patients who have been hospitalised with COVID-19 disease and who subjectively and objectively evidence cognitive impairment
- To assess cognitive performance in patients reporting cognitive deterioration following hospitalisation for COVID-19 disease
- To outline associations between MR Imaging and spectroscopy data and cognitive test performance

Primary Objective

To report the association (present or not) between MR imaging and spectroscopy measures and cognitive performance following hospitalisation for COVID-19 disease.

Secondary Objectives

To report the level of cognitive performance as measured by formal neuropsychometric assessment.

ENDPOINTS

Primary Endpoint

The primary endpoint is MR imaging and spectroscopy associations with measured cognitive performance.

Secondary Endpoint

[figure not shown]

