Once a patient has indicated that they are interested in participating in MR imaging and analysis the research nurse or team member will contact the patient. The research team member will provide them with a written and verbal explanation of the study aims and detail on the exact nature of the study, the implications and constraints of the protocol and any risks involved in taking part. It will be clearly stated that the individual is free to withdraw from the study at any time for any reason, without prejudice to future care, and with no obligation to give the reason for withdrawal. Written informed consent will be taken by a member of the research team trained in research consent procedures. This will be done face to face on the day of the study visit. Subsequent to this the research team member will get in contact to arrange the study visit.

PARTICIPANTS:

Inclusion Criteria

- A patient who has been hospitalised with COVID-19 disease (with a positive Polymerase Chain Reaction (PCR) result for SARS-CoV2 infection) within NHS Grampian hospitals with subsequent subjective reporting and objective evidence of cognitive change.
- Patients aged over 18.
- Patient has completed neuropsychometric testing protocol as described above.
- Participant who is willing and able to give informed consent for participation in the study.

Exclusion Criteria

- Any patient whose physical condition will preclude them from lying still for the duration of the brain scan.
- Contraindication to magnetic resonance scanning such as an implantable cardiac device.
- Patients who required intensive care treatment for SARS-CoV2 infection.

- Patients with a pre-existing diagnosis of a Neurodegenerative disease (eg. Dementia), Intellectual Disability, previous moderate/severe brain injury or previous brain injury with noted cognitive change.
- Patients with a pre-existing neuro-inflammatory disorder (eg. Multiple Sclerosis).
- Patients under investigation for, or with a history of, cognitive change prior to hospitalisation with COVID-19 disease.
- Patients with a dependency on alcohol or recreational drugs.

PROCEDURE:

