Participants who have expressed their interest to take part will be contacted by a member of the research team to discuss the date of their study visit, which will take place at the University of Aberdeen research MRI facility, Aberdeen Royal Infirmary Foresterhill. The potential participant will be asked about possible COVID-19 symptoms prior to proceeding with the study visit so as to ensure robust infection control measures.

Study visit:

The patient will be asked to sign an informed consent form to enter the study. This will be taken on the day of the scan.

Participants will be asked to complete an MRI safety questionnaire prior to the scanning visit and this will be checked again on the day of their study visit. They will be met by a researcher at the MRI facility and will be consented prior to scanning. The scan may involve the participant changing into some loose-fitting clothing, usually a set of scrubs. These will be provided for the participant on the day if needed.

During the study visit the following will take place:

Brain magnetic resonance imaging and spectroscopy

Brain MRIs will be performed using a Philips Ingenia dStream 3T scanner. The protocol will include high resolution structural images (3D T1-weighted, T2-weighted, susceptibility weighted imaging (QSM), fluid attenuated inversion recovery (FLAIR) and diffusion weighted imaging (DWI/DTI)) and a resting state functional sequence. These sequences allow us to detect clinically significant features such as lacunes, extended perivascular spaces, cortical and subcortical infarct, white matter hyperintensities and microbleeds. The 3D T1-weighted images will allow volumetric analysis while FLAIR images will allow quantification of white matter hyperintensity lesion load and DTI will enable computation of white matter structural integrity. Quantitative susceptibility mapping (QSM), sensitive to iron deposition, will be acquired with a multi-echo gradient-echo pulse sequence. Metabolic profile will be quantified from spectrum acquired using single voxel Point RESolved Spectroscopy (PRESS) sequence from 3 targeted regions previously reported to be involved in cognitive decline after COVID-19.

WITHDRAWAL PROCEDURES

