Participants are free to withdraw at any time during the study without having to give a reason. Should this occur, additional participants will be recruited to fill in the gaps, but this is not expected to be a significant number. Some participants may consent to participate but may not wish to have a particular test done. These patients will be excluded from the study.

DATA COLLECTION

Clinical data will be entered onto a CRF and then stored electronically on University of Aberdeen managed computer systems by the research team.

Results from the analysis of scans/cognitive tests will be stored electronically on University of Aberdeen and NHS Grampian managed computer systems by the research team. Anonymised data will be transferred between servers, where necessary, using the ZendTo software facility.

Data collected from participants will be stored in an anonymised fashion with the use of unique participant identification numbers. Relevant data will be exported into a csv file and analysed using R software. Consent forms pertaining to the study will be kept in a locked filing cabinet in the Aberdeen Biomedical Imaging Centre. Data generated in the study will be kept for a minimum of 6 years and [name] will act as custodian for the data.

The CI and study staff involved in this project will comply with the requirements of the General Data Protection Regulations (GDPR) and the Data Protection Act 2018. The Health Research Authority (HRA) recommended working to fulfil transparency requirements under the GDPR for health and care research has been included in the PIS.

The sponsor is responsible for ensuring that trial data is archived appropriately. Essential data shall be retained for a period of at least 6 years following close of study.

SAMPLE SIZE CALCULATION

The study, envisaged as a pilot will compare n=30 patients. We will recruit from the Mental Health After COVID-19 Hospitalisation Team (MACH). We will work to achieve full data for 30 patients and the retention rate is envisaged to be high given the single study visit. Retention should be further bolstered in that only patients who have already completed neuropsychometric testing will progress forward to have the MR imaging.

Power calculations: Sample size and power calculations are not possible at the pilot stage however our sample size of 30 will ensure a spread of measurements to allow us to estimate effects sizes and aid planning for future studies.

COMPLIANCE AND LOSS TO FOLLOW-UP

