In the STRADL study (Habota et al. 2019), where 1188 participants were tested, compliance was 90% for brain imaging, 97% for laboratory samples and 99% for cognitive tests. We expect similar compliance in the current study.

POTENTIAL RISKS AND HAZARDS

Magnetic resonance imaging is very safe and there are no known side effects. The scan is noisy and we provide headphones to protect the participants' ears. The study participant will be able to speak to the radiographer during the scan..

For female participants of child bearing age where there is a possibility of pregnancy there will be a requirement for a negative pregnancy test prior to undertaking the scan. If this is not possible the scanning will not go ahead.

It is possible that an unexpected health problem could be found on the tests. However, if this is the case, the participant will be notified and the results will be passed on to the participant's General Practitioner (GP) and/or other relevant health professional, along with any recommendations for treatment that may be necessary.

PROPOSED ANALYSES

Data will be analysed using R as follows. Using the multi-echo gradient echo phase and magnitude data we will determine a marker of in-vivo brain iron concentration by Quantitative Susceptibility Mapping (QSM) (Betts et al., 2016). Cortical sub-structures where associations have previously been found between cognitive performance and iron deposition (Spence et al., 2020) will be extracted from high resolution T1-weighted MR scans by the FreeSurfer image analysis suite. The mean iron induced susceptibility (a marker of iron concentration and therefore brain inflammation) in each cortical sub-structure will be determined. Morphological brain measures such as cortical and sub-cortical volumes will also be extracted. A composite score will be determined from the cognitive tests by principal component analysis. The spectrum will be processed in jMRUI software for phase correction, apodisation, with spectral peak amplitude of brain metabolites subsequently quantified using the Advanced Method for Accurate, Robust and Efficient Spectral fitting of MRS data with use of prior knowledge (AMARES) algorithm. Associations between cognitive performance, regional iron deposition, volume, markers of small vessel disease and brain metabolism will be determined using a general linear approach while correcting for confounding variables such as age and BMI.

STUDY MANAGEMENT AND OVERSIGHT ARRANGEMENTS

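### Excluding consented participants who decline one test discards cognitive scores already held for the secondary objective; an available-data rule would keep them at little cost

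*Protocol*

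**What the plan says.** The rule is in the Protocol, under Withdrawal Procedures. After dealing with participants who withdraw, who are to be replaced, the section turns to a different group: "Some participants may consent to participate but may not wish to have a particular test done. These patients will be excluded from the study". The exclusion is from the study as a whole, not from the analysis that the missing test would have served. No other section provides for keeping partial data.

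Four other places bear on it:

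- **Secondary Objectives:** "To report the level of cognitive performance as measured by formal neuropsychometric assessment". This needs no scan.
- **Inclusion Criteria:** "Patient has completed neuropsychometric testing protocol as described above". The sample size section repeats the order of events: "only patients who have already completed neuropsychometric testing will progress forward to have the MR imaging".
- **Procedure, Study visit:** "They will be met by a researcher at the MRI facility and will be consented prior to scanning". The only assessments listed for that visit are MR imaging and spectroscopy.
- **Sample Size Calculation** sets the target: "We will work to achieve full data for 30 patients". **Compliance and Loss to Follow-up** reports that in a cited cohort "compliance was 90% for brain imaging", and adds: "We expect similar compliance in the current study".

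**The concern.** The sequence is cognitive battery, then consent, then scan. Someone who consents and then declines a test is therefore most naturally declining an MR component, and their cognitive scores are already complete. Those scores are all that the secondary objective requires, yet the rule removes them. The summary of cognitive performance then describes only people willing to finish the scan visit. Recruiting replacements restores the number but not the excluded people's scores.

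The Protocol does not settle whether a test means the whole scan or also a single MR sequence. If it includes single sequences, the rule also discards MR measures that were acquired and could serve the separate associations listed under Proposed Analyses. If it means the whole scan, the loss falls on the secondary objective only.

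The study is a pilot meant to help plan later work. How many consented patients decline which component, and how they scored, is useful planning information. Nothing in the rule forbids reporting it, but nothing requires it either.

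**Working it through.** The target of 30 comes with no significance level, power, effect size or SD, so there is no calculation to reproduce. What can be sized is the effect of the exclusion rule.

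**Inputs**

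- Complete sets wanted: 30 (Sample Size Calculation).
- Imaging compliance: p = 0.90 (Compliance and Loss to Follow-up). A value of p = 0.95 is assumed as a milder case.
- The 99% cognitive-test compliance given in the same section is not applied, because testing is finished before consent.
- Difference in mean cognitive score between decliners and completers: not given. Assumed to be 0.25, 0.5 or 1.0 SD, in either direction.

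**Number lost before 30 complete sets**

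The number of non-completers met before the 30th completer is negative binomial, with mean 30(1 − p)/p.

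| Compliance | Mean lost | Chance of more than 4 |
|---|---|---|
| 0.90 | 30 × 0.10 / 0.90 = 3.33 | 0.250 |
| 0.95 (assumed) | 30 × 0.05 / 0.95 = 1.58 | 0.026 |

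At 0.90 the median is 3 and the 10th to 90th percentiles are 1 to 6. The simpler inflation agrees: 30/0.90 = 33.3, rounded up to 34 consented, so about 4 lost. The chance of at least one non-completer among 30 consented is 1 − 0.90^30 = 0.96.

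**Precision of a mean cognitive score**

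The 95% half-width in SD units is t(0.975, n − 1)/√n.

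| n | Half-width (SD) | Narrower than n = 30 |
|---|---|---|
| 30 | 0.373 | – |
| 33 | 0.355 | 5.0% |
| 34 | 0.349 | 6.6% |

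**Shift in the mean from leaving decliners out**

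The shift is the share excluded times the difference. With 10% excluded:

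- 0.10 × 0.25 = 0.025 SD
- 0.10 × 0.5 = 0.05 SD
- 0.10 × 1.0 = 0.10 SD

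All three lie well inside the half-width of 0.373 SD. Using 4 of 34 (11.8%) as the share gives 0.03 to 0.12 SD, which leads to the same conclusion.

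**Primary associations**

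These need MR and cognitive data from the same person. A participant with no scan contributes nothing, so the gain there is zero. A participant who declines one sequence could contribute to associations based on the sequences completed.

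**The case against.** The strongest reply is that this is a coherent complete-case design. The study is an imaging-association pilot, its primary endpoint needs both kinds of data, and recruiting until 30 sets are complete gives one cohort and one denominator throughout. Precision at the planned size is not reduced; only a small bonus is forgone. The Protocol sets out no estimate of a mean cognitive score: under Proposed Analyses cognition enters as a principal-component composite, and the secondary endpoints that can be read all need MR. The cohort is also already selected on suitability and willingness for scanning, so adding back three or four people barely changes that. Someone who refuses the whole scan has declined the only research procedure. Participant flow and analysis sets are commonly left to the SAP, which is not shown. Whether consent covers use of the scores without a scan cannot be checked.

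Much of this stands as a limit on size. The half-width of a mean is only a convenient yardstick for an objective that the Protocol states without an estimator. The 10% is an upper guide, because not all imaging non-compliance is refusal and the exclusion criteria already screen out MR contraindications and inability to lie still.

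It does not remove the point. Wanting 30 complete sets is a reason to keep recruiting, not a reason to discard other participants' scores from an objective that needs no scan. The exclusion is a firm rule in the Protocol, and an SAP could not easily restore people whom the Protocol has excluded from the study.

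**Conclusion.** The concern holds, as a minor point. The rule removes usable cognitive data from participants who have not withdrawn, and makes the secondary summary conditional on completing the scan visit. With the Protocol's own 90% compliance the expected loss is 3.3 participants, probably fewer in practice, and the cost in precision is 5% to 7% of the interval width. The possible shift in the mean is small beside the interval itself; it rests on assumed differences, since the Protocol gives none. The primary associations lose nothing from participants with no scan, and would lose something only if the rule also reaches single MR sequences. The reason to act is that the better rule is cheap and also yields planning information, not that any main result is at risk.

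**What to change.** Replace the exclusion sentence under Withdrawal Procedures with wording such as:

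> Participants who decline or do not finish a test remain in the study and, within the scope of their consent, contribute to every analysis for which they have data. The number analysed is reported for each measure, and the number declining each component is reported with a descriptive summary of their cognitive scores.

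This applies to those who decline a test, not to those who withdraw consent. Recruitment to 30 complete sets continues, and the conditions for scanning are unchanged.

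The cost is one sentence, a check that the consent wording covers use of the cognitive scores when a scan is declined, and the amendment approvals that the Protocol requires (Sponsor, REC and NHS R&D). The downside is that the number analysed will differ slightly between measures.

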The CI and study staff involved with this study will comply with the requirements of the UK Data Protection Laws with regard to the collection, storage, processing and disclosure of personal information and will uphold the Data Protection Act's core principles. The CI and study staff will also adhere, if appropriate, to the current version of the NHS Scotland Code of Practice on Protecting Patient Confidentiality. Access to collated participant data will be restricted to the CI and appropriate study staff.

Computers used to collate the data will have limited access measures via usernames and passwords.

Published results will not contain any personal data that could allow identification of individual participants.

Adverse Events

An adverse event (AE) is any untoward medical event affecting a study participant. Each AE will be considered for severity, causality or expectedness and may be reclassified as a serious event or reaction based on prevailing circumstances.

A serious adverse event (SAE) is any AE which;

- Results in death
- Is life threatening (i.e. the subject was at risk of death at the time of the event; it does not refer to an event which hypothetically might have caused death if it were more severe).
- Requires hospitalisation or prolongation of existing hospitalisation
- Results in persistent or significant disability or incapacity
- Is a congenital anomaly or birth defect

All AEs and SAEs will be recorded from the time a participant consents to join the study until the day of completion of their scan.

The Investigators will interrogate notes and other available clinical documentation, and sometimes question participants directly, to discern details of the occurrence of AEs/SAEs. If there is any doubt as to whether a clinical observation is an AE, the event should be recorded.

This is a low-risk study and involves no interventional procedures. Only AEs and SAEs directly linked to the undertaking of the MR imaging protocol will be recorded. All safety procedures and checks around MR imaging will be implemented and adhered to. [name] serves as MR safety expert for NHS Grampian.

In the event of an AE or SAE this will be recorded initially and then reported to the sponsor as per SOP UoA-NHSG-SOP-014. Follow up information will also be reported to the sponsor in line with the aforementioned SOP.

INSURANCE AND INDEMNITY

NHS Grampian is sponsoring the study.

Insurance:

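### Adverse events are sought from records and only sometimes by asking the participant, so minor events at the scan visit may be captured incompletely and unevenly

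*Protocol*

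**What the plan says.** All references are to the protocol.

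- **How events are found** (Good Clinical Practice, Adverse Events): "The Investigators will interrogate notes and other available clinical documentation, and sometimes question participants directly, to discern details of the occurrence of AEs/SAEs".
- **Window** (same section): recording starts at consent and runs "until the day of completion of their scan".
- **Start of the window** (Procedure, Study visit), on the consent form: "This will be taken on the day of the scan". Consent and Enrollment also places written consent on the day of the study visit, but its next sentence reads: "Subsequent to this the research team member will get in contact to arrange the study visit".
- **Scope** (Adverse Events), stated twice. First: "All AEs and SAEs will be recorded from the time a participant consents to join the study until the day of completion of their scan". Later: "Only AEs and SAEs directly linked to the undertaking of the MR imaging protocol will be recorded".

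Three other statements bear on the point. A researcher meets each participant at the MRI facility (Study visit). The participant can talk to the radiographer while being scanned (Potential Risks and Hazards). A clinical observation that may or may not be an adverse event is to be recorded (Adverse Events).

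**The concern.** The routine source does not match the events being looked for. What is to be recorded is, on the narrower statement, whatever the scan itself causes, on one day, at a research facility. Minor events of that kind, such as anxiety, discomfort or dizziness, are largely known only if the participant mentions them, and records kept for clinical care are an unlikely place to find them. The source that would reveal them, asking the participant, is used *sometimes*, for a subset that the protocol does not define.

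At stake is consistency of safety capture. If some participants are asked and others are not, the absence of a recorded event means two different things: asked and none reported, or not asked. A later reader of the results could not tell these apart, and a count would have no clear denominator.

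**Working it through.** The protocol states no adverse-event rate, detection probability or safety-based sample size, so there is no figure to reproduce. The check is mainly a comparison of texts.

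**1. Source.** "The Investigators will interrogate notes and other available clinical documentation" carries no condition and applies to everyone. The other half, "and sometimes question participants directly, to discern details of the occurrence of AEs/SAEs", is conditional, and the condition is not given.

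**2. Window.** It opens at consent and closes on the day of the scan. The Study visit text puts consent on that same day, so the window is one visit.

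**3. Does the point depend on the two internal conflicts?**

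| Reading | Effect on the point |
|---|---|
| Scan-linked events only, window is the visit | Records are a poor source for minor events; asking is the natural one |
| All events, window is the visit | Same, with a wider range of minor events that need asking |
| Consent precedes arranging the visit, so the window is longer | Records may cover the days before the scan better, but not what is felt at the scan |

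The point survives each reading. What changes is what counts as an event and when counting starts.

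**4. Why no size can be given.** Let *q* be the share of participants asked and *s* the share of events among those not asked that come to light anyway (seen, volunteered or documented). If asking finds every event, the fraction recorded is *q* + (1 − *q*)*s*. The protocol fixes neither quantity. With *q* = 0.5 as an assumption:

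- *s* = 0: 0.5 + 0.5 × 0 = 0.50
- *s* = 0.5: 0.5 + 0.5 × 0.5 = 0.75
- *s* = 1: 0.5 + 0.5 × 1 = 1.00

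The result runs from half the events to no loss at all, even with *q* held fixed.

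**5. Why the number asked is worth recording (illustration only).** Suppose no event is recorded. The one-sided 95% upper bound on the event rate, from *m* participants asked, is 1 − 0.05^(1/*m*):

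- *m* = 30: 9.5%
- *m* = 15: 18.1%
- *m* = 8: 31.2%

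Only the 30 comes from the protocol. The last two bounds are the extreme case in which participants who were not asked give no information (*s* = 0). With 15 asked and *s* = 0.5, the bound θ solves (1 − θ)^15 × (1 − θ/2)^15 = 0.05. Since 0.05^(1/15) = 0.819, this is (1 − θ)(1 − θ/2) = 0.819, which gives θ = 12.6%. The same zero count can thus support bounds from 9.5% upwards, depending on a number that the protocol does not require anyone to record.

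**The case against.** The strongest reply is that the visit is staffed from start to finish. A researcher meets each participant, the radiographer can be spoken to, and doubtful observations are to be recorded. An event that is seen or volunteered can be written down without any clinical note. The records clause is also wider than clinical notes alone, and can be read as a way to fill in details rather than as the only means of detection. Serious events, as the protocol defines them, are the kind that records do capture. The study is described as low-risk and MRI as having no known side effects. Adverse events do not appear in the aims, the objectives, the endpoints that can be read, or the Proposed Analyses.

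Most of this stands, and it rules out two stronger readings. A reader might infer that scan-related events *will* be undercounted. The documents do not show that: the routes just listed could pick up most or all events. A reader might also infer that the report will print no events in 30 and so overstate how well the scan was tolerated. No tolerability result is planned in the text; the pilot's stated purpose for later work is to estimate effect sizes.

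What the reply does not remove is the unevenness. The researcher is not told to ask, the radiographer link lets a participant speak but requires nobody to enquire, and the rule on doubtful cases applies to an observation already made. That minor scan events are mostly felt rather than seen, and seldom reach clinical notes, is a reasonable judgement and not a statement in the protocol.

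**Conclusion.** The point holds as a cheap improvement. Discretionary questioning, combined with a window that is in effect the scan visit, means that minor participant-felt events may be ascertained incompletely and inconsistently. Serious events are less affected, and the primary analysis of imaging and cognition is unaffected. The size of any undercount cannot be derived from the protocol; the figures above rest on assumed shares asked and volunteered and only show why the number asked matters.

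The conclusion rests on two assumptions: that clinical records say little about a research scan visit, and that no unwritten practice already has every participant asked. Separately, and on the text alone, the two scope statements conflict, and so do the two accounts of the order of consent and visit arrangement.

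**What to change.** 1. In Adverse Events, replace the clause on occasional questioning with a fixed rule: at the end of every study visit the researcher asks each participant the same open question about any problem during or since the scan, and enters the answer, including none, on the CRF. Keep the records review as a supplement.
2. Give any adverse-event count over the number of participants asked.
3. Reconcile the statement that all events are recorded with the statement that only scan-linked ones are, so that the scope is single.
4. Reconcile Consent and Enrollment with Study visit on whether consent comes before or after the visit is arranged, since this sets the start of the window.

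Cost: a sentence or two of protocol text and one CRF line. At about a minute each, the question takes some 30 minutes over 30 participants, from a researcher who already meets each one at the visit. A few more minor events will need recording. As a protocol change it needs the Sponsor, REC and R&D approvals that the protocol requires for amendments, so it is best bundled with any other amendment.
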